3.3 Subject included

No formal sample size calculation was done as this is an open-label extension trial.

Subjects with aPAP who have completed the IMPALA (MOL-PAP-002) trial will be eligible for this trial. Up to 90 subjects may be included. All subjects in need of treatment will receive inhaled molgramostim.

4 Analysis Sets

All subjects excluding screening failures will be included in the full analysis set.

All subjects with exposure within the trial will be included in the safety analysis set.

The full analysis set will be used for demographics and efficacy summaries and the safety analysis set will be used for safety summaries.

Only recorded data will be analyzed/presented and any subjects who have missing data will only have observed data reported, with no imputation for missing data.

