5.2 Data Issues due to Covid-19 Pandemic

To get an overview of the impact the COVID-19 pandemic has on the trial the below output will be presented

- Listing with COVID-19 positive subjects including country and time since trial start to COVID-19 start date
- Listing of all adverse events occurring in COVID-19 positive patients including time of the adverse event relative to the COVID-19 start date
- Table with number of missed key secondary endpoints assessments due to pandemic by treatment and visit. The key secondary endpoints are (A-a)DO₂, 6MWD, SGRQ total, DLCO (% predicted), PaO₂ and DSS
- Table with number of alternative endpoint ascertainment (telephone visits, allowed out of window visits and such) if any due to COVID-19 by treatment and visit
- Listing with all protocol deviations due to COVID-19

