- Listing 16.2.6.8 Individual overall clinical assessments (all subjects)
- Listing 16.2.6.9 Individual GM-CSF measurements above lower level of quantification (all subjects)
- Listing 16.2.7.1 Adverse events (all subjects)
- Listing 16.2.7.2 Serious adverse events (all subjects)

Listing 16.2.7.3 Adverse drug reactions (all subjects)

Listing 16.2.7.4 Adverse events leading to treatment discontinuation (all subjects)

Listing 16.2.8.1 Individual haematology (all subjects)

Listing 16.2.8.2 Individual clinical chemistry (all subjects)

Listing 16.2.9.1 Individual vital signs (all subjects)

Listing 16.2.9.2 Individual electrocardiogram (all subjects)

Listing 16.2.10.1 Individual CT scans (all subjects)

13 List of Tables

Section 14.1

Table 14.1.1 Subject disposition (full analysis set)

Table 14.1.2 Number of subjects by visit (full analysis set)

Table 14.1.3 Baseline demographics (full analysis set)

Table 14.1.4 Medical history (full analysis set)

Table 14.1.5 Summary of exposure (months) (safety analysis set)

Table 14.1.6 Summary of cumulative exposure (safety analysis set)

Table 14.1.7 Summary of relative exposure (safety analysis set)

Table 14.1.8 Summary of last visit attended (full analysis set)

Table 14.1.9 Concomitant medication (safety analysis set)

Table 14.1.10. Summary of missed key secondary endpoints assessments due to COVID-19 pandemic (safety analysis set)

Table 14.1.11 Summary of alternative endpoint ascertainment due to COVID-19 pandemic (safety analysis set)

Section 14.2

(14.2.1: Blood gas analysis endpoints)

Table 14.2.1.1 Summary of (A-a)DO₂ (mmHg) (full analysis set)

Table 14.2.1.2 Summary of change from baseline in (A-a)DO₂ (mmHg) (full analysis set)

(14.2.2: 6 minutes walking test endpoints)

Table 14.2.2.1 Summary of 6 minutes walking distance (m) (full analysis set)

Table 14.2.2.2 Summary of change from baseline in 6 minutes walking distance (m) (full analysis set)

Table 14.2.2.3 Summary of pre-walk dyspnoea score (Borg CR10) (full analysis set)

Table 14.2.2.4 Summary of change from baseline in 6 minutes walking distance (m) (full analysis set)

Table 14.2.2.5 Summary of post-walk dyspnoea score (Borg CR10) (full analysis set)

Table 14.2.2.6 Summary of change from baseline in dyspnoea score (Borg CR10) (full analysis set)

Table 14.2.2.7 Summary of SpO₂ at start of walk (%) (full analysis set)

Table 14.2.2.8 Summary of change from baseline in SpO₂ at start of walk (%) (full analysis set)

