Table 14.2.2.9 Summary of worst SpO₂ during walk (%) (full analysis set)

Table 14.2.2.10 Summary of change from baseline in worst SpO₂ during walk (%) (full analysis set)

Table 14.2.2.11 Summary of desaturation during walk (%) (full analysis set)

Table 14.2.2.12 Summary of change from baseline in desaturation during walk (%) (full analysis set)

Table 14.2.2.13 Summary of completion of 6 minutes walking test (full analysis set)

(14.2.3: SGRQ endpoints)

Table 14.2.3.1 Summary of SGRQ total score (full analysis set)

Table 14.2.3.2 Summary of change from baseline in SGRQ total score (full analysis set)

Table 14.2.3.3 Summary of SGRQ symptoms score (full analysis set)

Table 14.2.3.4 Summary of change from baseline in SGRQ symptoms score (full analysis set)

Table 14.2.3.5 Summary of SGRQ activity score (full analysis set)

Table 14.2.3.6 Summary of change from baseline in SGRQ activity score (full analysis set)

Table 14.2.3.7 Summary of SGRQ impact score (full analysis set)

Table 14.2.3.8 Summary of change from baseline in SGRQ impact score (full analysis set)

(14.2.4: Whole lung lavage endpoints)

Table 14.2.4.1 Summary of number of subjects with a whole lung lavage between IMPALA and IMPALA-Z (safety analysis set)

Table 14.2.4.2 Summary of whole lung lavage (safety analysis set)

Table 14.2.4.3 Summary of whole lung lavage by location (safety analysis set)

Table 14.2.4.4 Summary of volume of saline used during whole lung lavage (L) (safety analysis set)

(14.2.5: Lung function test endpoints)

Table 14.2.5.1 Summary of DLCO (%) (full analysis set)

Table 14.2.5.2 Summary of change from baseline in DLCO (%) (full analysis set)

Table 14.2.5.3 Summary of FEV1 (%) (full analysis set)

Table 14.2.5.4 Summary of change from baseline in FEV1 (%) (full analysis set)

Table 14.2.5.5 Summary of FVC (%) (full analysis set)

Table 14.2.5.6 Summary of change from baseline in FVC (%) (full analysis set)

(14.2.6: Disease severity score)

Table 14.2.6.1 Summary of disease severity score (full analysis set)

Table 14.2.6.2 Summary of change in disease severity score compared to baseline (full analysis set)

(14.2.7: Supplemental oxygen during trial)

Table 14.2.7.1 Summary of oxygen supplement anytime during the trial (full analysis set)

Table 14.2.7.2: Summary of oxygen supplement ongoing at baseline (full analysis set)

Table 14.2.7.3: Summary of oxygen supplement ongoing at end of trial (full analysis set)

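### The whole lung lavage tables put a secondary efficacy endpoint on the safety set, against SAP Section 4 and with no declared exception; two COVID-19 tables carry the same label

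*SAP*

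**What the plan says.** SAP Section 4 defines two nested populations. For the full analysis set (FAS): "All subjects excluding screening failures will be included in the full analysis set". For the safety set: "All subjects with exposure within the trial will be included in the safety analysis set". It then allocates them: "The full analysis set will be used for demographics and efficacy summaries and the safety analysis set will be used for safety summaries".

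Lavage frequency is a secondary endpoint in protocol Section 5.3.2 and SAP Section 7.2, and the protocol places lavage under efficacy assessments (Section 10.7.7). SAP Section 7.2.4 asks for the number of subjects, the number of events and a negative binomial event rate with a 95% interval. The rate is adjusted for time in trial, counted from visit 1 to the end-of-trial date.

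In SAP Section 13 all four lavage tables are labelled with the safety set, for example "Table 14.2.4.2 Summary of whole lung lavage (safety analysis set". The other efficacy tables are on the FAS, for example "Summary of change from baseline in (A-a)DO₂ (mmHg) (full analysis set".

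SAP Section 5.2 also plans two COVID-19 tables. One is described as "Table with number of missed key secondary endpoints assessments due to pandemic by treatment and visit"; the other counts alternative ascertainment. Section 5.2 names no population for either. Section 13 lists them as "Summary of missed key secondary endpoints assessments due to COVID-19 pandemic (safety analysis set" (Table 14.1.10) and "Summary of alternative endpoint ascertainment due to COVID-19 pandemic (safety analysis set" (Table 14.1.11).

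SAP Section 9 explains that a safety set was added because some subjects are untreated in this trial. It does not say that any secondary endpoint was moved to it. Protocol Section 11 says that all subjects enter the data presentations.

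**The concern.** One secondary endpoint is tabulated on a smaller population than the rest, with no reason given. A subject who was followed from visit 1 but never took molgramostim in this trial counts in the oxygenation, walking-distance, quality-of-life and lung-function tables. The same subject is absent from the lavage tables. Any lavage in such a subject is left out of the event count, and that subject's follow-up is left out of the denominator, so both the rate and its interval depend on an undeclared choice.

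Table 14.2.4.1 makes this plainest. It counts lavages done between the two trials, and restricting it to subjects exposed later selects on something that happened after the events being counted.

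The COVID-19 tables raise a smaller issue. They describe how efficacy endpoints came to be missed or collected differently, but they omit the never-exposed subjects whom the endpoint tables include.

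**Working it through.** **1. Labels against the rule (SAP Sections 4 and 13)**

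| Output | Set in Section 13 | Set under Section 4 |
|---|---|---|
| (A-a)DO2, 6MWD, SGRQ, DLCO, FEV1, FVC, DSS | FAS | FAS |
| Lavage, 14.2.4.1 to 14.2.4.4 | Safety | FAS (secondary efficacy endpoint) |
| Subjects by visit 14.1.2; last visit 14.1.8 | FAS | Not explicit |
| COVID-19, 14.1.10 and 14.1.11 | Safety | Not explicit |

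The lavage tables conflict with the rule directly. For the COVID-19 tables the rule does not settle the matter.

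**2. Size of the population gap**

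The plan gives no sample-size or power figure to reproduce. Its own split adds up: 55 on treatment + 5 off treatment = 60 enrolled (SAP Section 3.2).

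Let k be the number never exposed in this trial. The 55 on treatment are exposed by definition, so k ≤ 5. Section 9 says that some subjects are untreated, so k ≥ 1. This takes the 55/5 split at face value and assumes that none of the 60 is a screening failure.

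| k | Safety set, 60 − k | Share of FAS omitted, k/60 |
|---|---|---|
| 1 | 59 | 1.7% |
| 2 | 58 | 3.3% |
| 3 | 57 | 5.0% |
| 4 | 56 | 6.7% |
| 5 | 55 | 8.3% |

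The tables are also split by IMPALA arm. Arm sizes in this trial are not given, so the omitted share in a single column could exceed the share in the total.

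**3. What this can do to the lavage rate**

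Assume equal follow-up per subject. Let ρ be the lavage rate in never-exposed subjects divided by the rate in exposed subjects. Then

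FAS rate / safety-set rate = (60 − k)/60 + (k/60)ρ = 1 + (k/60)(ρ − 1).

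- k = 5, ρ = 0: 1 − 5/60 = 0.917
- k = 5, ρ = 1: 1.000
- k = 5, ρ = 2: 1 + 5/60 = 1.083
- k = 1, ρ = 0 or 2: 0.983 or 1.017

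The documents give no value for ρ. Subjects left untreated because of remission would point below 1, but that is not established, so the direction is open.

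**4. What this can do to the proportion with a lavage**

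Take k = 5 and an assumed m exposed subjects with at least one lavage. The FAS range runs from none to all 5 never-exposed subjects having one.

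| m | Safety set, m/55 | FAS, m/60 to (m + 5)/60 |
|---|---|---|
| 5 | 9.1% | 8.3% to 16.7% |
| 10 | 18.2% | 16.7% to 25.0% |
| 20 | 36.4% | 33.3% to 41.7% |

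**5. COVID-19 tables**

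Six key endpoints × 60 subjects = 360 possible assessments per visit. Of these, 6k fall outside Table 14.1.10: 6 for k = 1, 30 for k = 5. This measures the table's scope and does not estimate how many assessments were missed.

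**The case against.** **Lavage.** The best defence is that the objective concerns lavage during use of the drug, so a never-exposed subject has nothing to contribute. SAP Section 7.2.4 gives some support, since its text describes the model offset as the log of exposure time. Two lavage tables also belong to the safety update in SAP Section 8.2.

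Little of this stands:
- The oxygenation, exercise, quality-of-life and lung-function objectives are worded in the same way, and their tables are on the FAS.
- The safety set does not isolate time on drug: a subject exposed once contributes all of their time in trial.
- Section 7.2.4 itself defines the denominator as time in trial, which every FAS subject has. The offset description is at odds with that.
- DSS Table 14.2.6.1 is in the same safety update and stays on the FAS. Lavage is not among the safety parameters in SAP Section 8.1.

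What does stand is that a summary in treated subjects is of interest, and that the data are not lost. Listing 16.2.6.4 covers all subjects, and Table 14.2.8.2, on the FAS, has lavage as a category of treatment required. Neither gives an event rate.

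**COVID-19 tables.** The defence is stronger here. These are trial-conduct counts placed in Section 14.1, Section 5.2 names no set, and Listing 16.2.4.6 shows COVID-19 deviations for all subjects. This is a poor fit with the endpoint tables and not a plain breach of Section 4.

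A reader might infer that missingness is counted on the wrong subjects. The safety set lies inside the FAS, so no ineligible subject is added; never-exposed subjects are left out. Only Table 14.1.10 counts missed assessments; Table 14.1.11 counts alternative ascertainment.

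A reader might also infer that the label alone stops these tables reconciling with the efficacy tables. They would not generally reconcile on the FAS either. Table 14.1.10 counts only pandemic-related misses, the (A-a)DO2 and DSS summaries also drop visits on supplementary oxygen, and PaO2 has no listed summary table.

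**Conclusion.** The lavage tables conflict with SAP Section 4 and with protocol Section 11, and SAP Section 9 does not declare it. Reported lavage counts, rate and interval can change as a result. The point is minor in size: at least one subject by implication of Section 9, and at most 5 of 60 (8.3%). With equal follow-up and k = 5, the rate would shift by about 8% if never-exposed subjects had either no lavages or twice the rate of exposed subjects.

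It would be tempting to read the 5 untreated subjects as never treated. The SAP says only that they were off treatment when the trial was terminated. Subjects could stop molgramostim and stay in the trial, and anyone exposed earlier in it belongs to the safety set. Five is therefore an upper bound. For the same reason, and because the number of pandemic-affected visits is not given, no total of uncounted missed assessments can be derived.

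For the COVID-19 tables the conclusion is limited to consistency of population. No efficacy estimate depends on them.

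**What to change.** 1. Produce Tables 14.2.4.1 to 14.2.4.4 on the FAS, as SAP Section 4 and protocol Section 11 require. A safety-set version may be kept as a labelled supplement.
2. In SAP Section 7.2.4, describe the offset as the log of time in trial, matching the definition given there. If exposure time were used, never-exposed subjects would have no usable offset and would drop out of the model even after the population flag is changed.
3. Relabel Tables 14.1.10 and 14.1.11 to the FAS so that they cover the same subjects as the endpoint tables.
4. State the number of subjects never exposed in this trial, so that the gap between the two sets is visible.

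The cost is table titles, a population flag and a wording correction. No new data are needed.
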